2.0 Clinical Investigation Plan Synopsis

Title	A safety and effectiveness trial for a leadless pacemaker system – The LEADLESS II Study
Investigational Device	Nanostim™ Leadless Pacemaker (LP)
Regulatory Classification of the Investigational Device	Class III
Number of Institutions	Up to sixty sites worldwide with up to 50 investigation sites in the United States.
Number of Subjects	Up to 667. At least 50% of the subjects recruited from sites located in the United States.
Trial Population	Subjects who are at least 18 years old, and who are indicated for a VVI(R) pacemaker.
Schedule of Assessments	Enrollment, Implant, Pre-Discharge, 2-week, 6-week, 3-month, 6-month follow-up, and every 6 months thereafter until study completion. Subjects consent to continue in post-approval studies and will have follow-ups at one year and each year thereafter until seven years after implant.
Study Design	Prospective, non-randomized, single-arm, international multicenter, clinical safety and effectiveness investigation.
Study Objective	The primary objectives of this study are to evaluate the clinical safety and effectiveness of the Nanostim™ LP system in subjects who are indicated for VVI(R) pacemaker.
Primary Safety Endpoint	The primary safety endpoint evaluates the 6-month complication-free rate.
Primary Effectiveness Endpoint	The primary effectiveness endpoint evaluates pacing thresholds and R-wave amplitudes within the therapeutic range through 6 months post-implant.

Clinical Investigation Plan

Secondary Endpoint	The secondary endpoint evaluates an appropriate and proportional rate response during graded exercise testing (CAEP protocol), performed between 3-month and 6-month visit.
PMA Application	[REDACTED]
Study continuation and supplementary analyses after PMA application	[REDACTED]

Clinical Investigation Plan

Inclusion Criteria	
Eligible subjects will meet all of the following:
 
1. Subject must have one of the clinical indications before device implant in adherence with Medicare, ACC/AHA/HRS/ESC single chamber pacing guidelines including:
 Chronic and/or permanent atrial fibrillation with 2 or 3° AV or bifascicular bundle branch block (BBB block), including slow ventricular rates (with or without medication) associated with atrial fibrillation; or Normal sinus rhythm with 2 or 3° AV or BBB block and a low level of physical activity or short expected lifespan (but at least one year); or Sinus bradycardia with infrequent pauses or unexplained syncope with EP findings; and2. Subject ≥ 18 years of age; and3. Subject has life expectancy of at least one year; and4. Subject is not enrolled in another clinical investigation; and5. Subject is willing to comply with clinical investigation procedures and agrees to return for all required follow-up visits, tests, and exams; and6. Subject has been informed of the nature of the study, agrees to its provisions and has provided written informed consent, approved by the IRB; and7. Subject is not pregnant and does not plan to get pregnant during the course of the study.
--------------------	--

Clinical Investigation Synopsis continued

Clinical Investigation Plan

Exclusion Criteria	
Subjects will be excluded if they meet any of the following:
 
 1. Subject has known pacemaker syndrome, has retrograde VA conduction or suffers a drop in arterial blood pressure with the onset of ventricular pacing; or 2. Subject is allergic or hypersensitive to <1 mg of dexamethasone sodium phosphate; or 3. Subject has a mechanical tricuspid valve prosthesis; or or 4. Subject has a pre-existing endocardial pacing or defibrillation leads; or 5. Subject has current implantation of either conventional or subcutaneous implantable cardioverter defibrillator (ICD) or cardiac resynchronization therapy (CRT); or 6. Subject has an implanted vena cava filter; or 7. Subject has evidence of thrombosis in one of the veins used for access during the procedure; or 8. Subject had recent cardiovascular or peripheral vascular surgery within 30 days of enrollment; or 9. Subject has an implanted leadless cardiac pacemaker.
Enrollment	Subjects who sign an IRB-approved informed consent and have an attempted or successful implant will be considered enrolled in the study.
Estimated Schedule	
Continued Access Phases (CAP)	
The CAP study will begin only after completion of enrollment of 667 patients in the IDE; the CAP cohort will follow the same schedule of evaluations as the IDE investigational plan except for the chronotropic assessment exercise protocol (CAEP) and the 24-hour Holter Monitor sub-studies.
 
The maximum sample size for this IDE including CAP will be 1567.

Clinical Investigation Plan

Clinical Investigation Synopsis continued

Schedule of Assessments	
Pre-procedure Assessments
 
• Inclusion/exclusion criteria• Informed consent• Pregnancy assessment• 12-lead ECG• Medical history• Medications¹ 
Implant Assessments
 
• Femoral vein assessment and access• Procedure details• Nanostim™ LP implant• Nanostim™ LP assessment and programming• Assess for changes in medications or change in therapy• Assess for AEs 
Post-procedure Assessments
 
• Access-site assessment• 12-lead ECG• X-ray of pacemaker• Nanostim™ LP assessment and programming• Assess for changes in medications or change in therapy• Assess for AEs 
2-week Visit
 
• Nanostim™ LP assessment and programming• Assess for changes in medications or change in therapy• Assess for AEs
-------------------------	--

¹ Data are collected for beta blocker, ACE, ARB, anti-arrhythmic, anti-coagulant, and anti-platelet medications, at all visits.

Clinical Investigation Plan

Clinical Investigation Synopsis continued

Schedule of Assessments (continued)	
6-week Visit
 
• Nanostim™ LP assessment and programming• Assess for changes in medications or change in therapy• Assess for AEs 
3-month Visit
 
• Nanostim™ LP assessment and programming• Assess for changes in medications or change in therapy• Assess for AEs• 24-hour Holter monitor with diary (30 subjects)• Graded exercise test (CAEP protocol) until 30 subjects provide data contributing to the analysis) 
6-month Visit
 
• Nanostim™ LP assessment and programming• Assess for changes in medications or change in therapy• Assess for AEs 
Every 6-month Visits
 
• Nanostim™ LP assessment and programming• Assess for changes in medications or change in therapy• Assess for AEs
--	---

Clinical Investigation Plan

Table 1: Schedule of Assessments

Activity	Pre-procedure Assessments		Procedure Assessment	Post-procedure Assessments							Additional Visits
	Screen & Enroll	Baseline		Implant	Post-procedure Assessment	2-week Follow-up Visit ¹	6-week Follow-up Visit ¹	3-month Follow-up Visit ²	6-month Follow-up Visit ²	Every 6-months until study completion ³	
Inclusion Exclusion	✓										
Informed Consent	✓										
Pregnancy Assessment/Test	✓										
Medical History		✓									
Baseline Assessment		✓									
Procedure			✓								
Post-procedure Pre-discharge					✓						
Nanostim™ LP Assessment and Programming				✓	✓	✓	✓	✓	✓	✓	✓
12-lead ECG			✓		✓						
X-ray of a pacemaker					✓						
Follow-up Visit						✓	✓	✓	✓	✓	
24-hour Holter monitor with diary⁴								✓			
Graded exercise test CAEP Protocol⁵								✓			
EQ-5D patient survey					✓	✓	✓	✓			
Additional CRFs (when applicable)											
Adverse Event			✓		✓	✓	✓	✓	✓	✓	✓
Deviation		✓	✓		✓	✓	✓	✓	✓	✓	
Study Withdrawal					✓	✓	✓	✓	✓	✓	
Product Out of Service			✓		✓	✓	✓	✓	✓	✓	
System Revision					✓	✓	✓	✓	✓	✓	
Death			✓		✓	✓	✓	✓	✓	✓	
Healthcare Utilization					✓	✓	✓	✓	✓	✓	

1 ±7 days

2 ±30 days

3 ±45 days

4 All capable subjects are asked to wear a 24-hour Holter and complete a diary, until 30 subjects provide data contributing to the analysis. The preferred window to perform the 24 hour Holter test is between the 3-month and 6-month visit.

5 All capable subjects are asked to perform a CAEP treadmill test until 30 subjects provide data contributing to the analysis. The preferred window to perform the CAEP treadmill test is between the 3-month and 6-month visit.

Clinical Investigation Plan

3.0 Abbreviations

Abbreviation	Definition	Abbreviation	Definition
2°	Second degree	EP	Electrophysiology
3°	Third degree	ESC	European Society of Cardiology
ACC	American College of Cardiology	ICD	Implantable cardioverter defibrillator
ACT	Activated clotting time	IFU	Instructions for use
ADL	Activities of daily living	INR	International normalized ratio
AE	Adverse event	IRB	Independent or institutional review board
AHA	American Heart Association	LP	Leadless pacemaker
AV	Atrioventricular	MRI	Magnetic resonance imaging
BBB	Bifascicular bundle branch	PA	Pulmonary arterial
CAEP	Chronotropic assessment exercise protocol	PtIr	Platinum Iridium
CFR	Complication free rate	RR	Rate response
CIP	Clinical investigation plan (also referred to as clinical protocol)	RV	Right ventricular
CRF	Case report form	SAE	Serious adverse event
CRT	Cardiac resynchronization therapy	TiN	Titanium nitride
ECG	Electrocardiogram	UADE	Unanticipated adverse device effect

Clinical Investigation Plan

4.0 Introduction

Sponsor has developed a leadless pacemaker system (Nanostim™ LP) to eliminate leads, pockets, and connectors required by conventional pacemakers and to eliminate associated complications. This concept could improve patient comfort by replacing a surgical procedure with a percutaneous one, eliminating the visible lump and scar at a conventional pacemaker's pectoral implant site, and removing the need for activity restrictions to prevent dislodgement after implantation of a conventional lead. Finally, the concept could permit pacemaker patients to undergo magnetic resonance imaging (MRI) with specified machines, although this is not being evaluated under this protocol.

St. Jude Medical's Nanostim™ LP system consists of a pacemaker and its accessories: a programmer, introducer, delivery catheter, and retrieval catheters. The accessories are not intended for use alone or with any device other than the Nanostim™ LP. The pacemaker and all accessories, except the programmer, are single-use devices and are supplied sterile.

5.0 Purpose

The intent of this IDE study is to evaluate the safety and effectiveness of the implanted Nanostim™ LP for treatment of bradycardia. A Nanostim™ Programmer Link also investigational, will be used in conjunction with the Nanostim™ LP. The Nanostim™ Programmer Link is a programming device that when connected to the St. Jude Medical™ Merlin™ Patient Care System (Model 3650) allows the user to communicate with the Nanostim™ LP.

6.0 Clinical Protocol

6.1 Study Design and Scope

This is a prospective, non-randomized, multi-center, international clinical study designed to evaluate the safety and effectiveness of the Nanostim™ LP System in a subject population indicated for a VVI(R) pacemaker.

Sponsor will conduct the study at up to 60 centers worldwide with up to 50 centers in the United States. To meet study endpoints, the Sponsor expects to enroll up to 667 subjects [REDACTED]

[REDACTED] Sponsor will allow a maximum of 100 (15% of the total) enrollments per center [REDACTED]

[REDACTED] At least 50% of subjects will be recruited from sites located in the United States.

Clinical Investigation Plan

Enrollment in the LEADLESS II clinical study [REDACTED]

[REDACTED] All eligible subjects will undergo implant attempt with a Nanostim™ LP.

All subjects will consent to continue annual follow-ups each year until 7 years after implant, in a long-term post-approval study.

The following study evaluations will occur after implant:

- Pre-discharge assessment
- 2-week follow-up visit (in-office or clinic)
- 6-week follow-up visit (in-office or clinic)
- 3-month follow-up visit (in-office or clinic)
- 6-month follow-up visit (in-office or clinic)
- Every 6 months thereafter until study completion
- Subjects consent to continue in post-approval studies and will have follow-ups at one year and each year thereafter until seven years after implant.

Follow-up schedules will be calculated from the date of successful implant.

6.2 Study Objective and Endpoints

The primary objectives of this study are to assess the safety and effectiveness of the Nanostim device from implant through 6-months in a subject population indicated for a VVI(R) pacemaker.

Primary Safety Endpoint

The primary safety endpoint evaluates a 6-month complication-free rate based on CEC adjudication of the adverse event.

Primary Effectiveness Endpoint

The primary effectiveness endpoint evaluates pacing thresholds and R-wave amplitudes within the therapeutic range through 6 months post-implant.

Secondary Endpoint

The secondary effectiveness endpoint evaluates an appropriate and proportional rate response during graded exercise testing (CAEP protocol).

Supplementary Safety Endpoint

The supplementary safety endpoint evaluates a 1-year complication-free rate based on CEC adjudication of the adverse event.

Clinical Investigation Plan

Supplementary Effectiveness Endpoint

The supplementary effectiveness endpoint evaluates pacing thresholds and R-wave amplitudes within the therapeutic range through 1 year post-implant.

6.2.1 Primary Endpoints

6.2.1.1 Primary Safety Endpoint

The goal of the primary safety endpoint evaluation is to demonstrate an acceptable complication-free rate (CFR); including any complication that prevents initial implantation.

Subjects whose initial implantation procedure was not successful will not be eligible for re-implantation attempts with the investigational device at a later date.

Subjects who leave the study before their 6-month visit will be censored at the time they leave the study. So, any complications that occur in subjects that leave the study before their 6 month visit will be included in this analysis.

Primary Safety Endpoint Evaluation at 6 Months

H_0 : CFR $\leq 86\%$ vs. H_1 : CFR $> 86\%$

A sample size of 300 evaluable subjects [REDACTED] establishing a two-sided 95% confidence interval for CFR, with a lower bound exceeding 86%, based on an exact binomial distribution.

[REDACTED]

Clinical Investigation Plan

[REDACTED]

[REDACTED]

[REDACTED]

[REDACTED]

6.2.1.2 Primary Effectiveness Endpoint

The composite primary effectiveness endpoint will be used to evaluate pacing thresholds and R-wave amplitudes at the 6-month visit and to document the percentage of subjects with acceptable sensing and pacing performance. Pacing thresholds and R-wave amplitudes will be collected, tabulated for each visit, and also displayed as frequency plots. Acceptable ranges for sensing and pacing are shown in the table below.

Table 2: Acceptable Ranges for Sensing and Pacing

Parameter	Acceptable test values
Pacing voltage	Pacing threshold < 2.0 V at 0.4 ms
R Sensitivity	R-wave amplitude > 5.0 mV or > value at implant

Success Criteria: A subject will be considered to have met the primary effectiveness endpoint if the pacing threshold voltage is \leq 2.0 V at 0.4 ms and the sensed R-wave amplitude is either \geq 5.0 mV at the 6-month visit or \geq the value at implant.

[REDACTED]

[REDACTED]

Clinical Investigation Plan

The inability to sense or pace within the programmable range available in the Nanostim™ LP device, resulting in device repositioning, replacement, or removal will be captured in the associated safety endpoints.

Primary Effectiveness Endpoint Evaluation at 6 Months

H_0 : Rate $\leq 85.0\%$ vs. H_1 : Rate $> 85.0\%$

A sample size of 300 subjects [REDACTED] establishing a two-sided 95% confidence interval for conformance with the above-referenced criteria for pacing threshold and R-wave amplitude, with a lower bound exceeding 85.0%, based on an exact binomial distribution.

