6.4.5.2 Pre-Discharge Assessment

Investigator will assess all subjects at the implant center prior to hospital discharge, or within 2-days post implant, whichever is shorter. Investigation team will:

- Assess for adverse events and deviations from investigation plan;
- Assess for changes in beta blockers, ACE, ARB, anti-coagulants, anti-platelets, anti-arrhythmics ;
- Measure and record Nanostim™ LP performance, as described in 6.4.3.3 Nanostim™ LP Assessment and Programming;
- Assess magnet mode;
- Program Nanostim™ LP per physician discretion;
- Obtain a 12-lead electrocardiogram (ECG) with pacing ON;
- Obtain a posterior/anterior (P/A) and lateral view chest x-ray to assess final LP position;
- Investigator will use medical judgment and provide institutional standard of care for post-pacemaker-implant monitoring.
- Collect medical billing information for implant (i.e. UB04 billing form)

Clinical Investigation Plan

Data Submission

Complete and submit the following case report forms and device print outs to St. Jude Medical, Sylmar, CA using the EDC system.

- Pre-Discharge Form (includes medication changes)
- Nanostim™ LP Assessment and Programming Form
- EQ-5D patient survey
- Study Withdrawal Form, if applicable
- Adverse Event Form, if applicable
- Deviation Form, if applicable
- Product Out of Service Form, if applicable
- System Revision Form, if applicable
- Death Form, if applicable

6.4.5.3 2-week and 6-week follow-up visits

All subjects will return to the investigation site for a 14-day and 42-day (± 7 days) follow-up visit. During this visit, investigation team will:

- Assess for adverse events and deviations from investigation plan;
- Assess for changes in beta blockers, ACE, ARB, anti-coagulants, anti-platelets, anti-arrhythmics ;
- Measure and record LP performance, as described in 6.4.3.3 Nanostim™ LP Assessment and Programming;
- Program Nanostim™ LP and adjust programmable parameters of Nanostim™ LP, as needed.

Data Submission

Complete and submit the following case report forms and device print outs to St. Jude Medical, Sylmar, CA using the EDC system.

- Follow-up Visit Form (includes medication changes)
- Nanostim™ LP Assessment and Programming Form
- EQ-5D patient survey
- Study Withdrawal Form, if applicable
- Adverse Event Form, if applicable
- Deviation Form, if applicable
- Product Out of Service Form, if applicable
- System Revision Form, if applicable

Clinical Investigation Plan

- Death Form, if applicable

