22.0 Publications

This study will be posted on ClinicalTrials.gov and results will be posted on ClinicalTrials.gov as required.

Clinical Investigation Plan

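### Is primary effectiveness scored at the 6-month visit, or over all visits up to 6 months as the summaries suggest?

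*Combined protocol and SAP*

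**What the plan says.** The synopsis (2.0) and section 6.2 use the same summary line: the primary effectiveness endpoint "evaluates pacing thresholds and R-wave amplitudes within the therapeutic range through 6 months post-implant".

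Section 6.2.1.2, where the endpoint is defined, opens by saying that the composite "will be used to evaluate pacing thresholds and R-wave amplitudes at the 6-month visit". It then deals with the other visits: "Pacing thresholds and R-wave amplitudes will be collected, tabulated for each visit, and also displayed as frequency plots".

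Its success sentence begins "A subject will be considered to have met the primary effectiveness endpoint if the pacing threshold voltage is" and gives a limit of 2.0 V at 0.4 ms with no visit. It continues with the R-wave, which must reach "5.0 mV at the 6-month visit or" be at least the implant value. Blacked-out text follows.

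The hypotheses (rate of 85.0% or less against more than 85.0%) stand under a heading that places the evaluation at 6 months. Section 6.2.1.3 says that the primary endpoints are tested against their goals at 6 months with exact binomial tests.

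**The concern.** A rate of being in range at one visit is not the rate of staying in range up to that visit. The second can never exceed the first. The gap is the share of subjects who are in range at month 6 but were out of range earlier.

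The summary wording has content to draw on. Device measurements are scheduled at implant, pre-discharge, 2 weeks, 6 weeks, 3 months and 6 months; for the 2-week and 6-week visits, section 6.4.5.3 says "Measure and record LP performance, as described in 6.4.3.3". An analyst who took the synopsis literally could build an every-visit responder rule and obtain a lower rate than one who followed 6.2.1.2. A reader of posted results (section 22.0) could take a month-6 rate for sustained performance.

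The success sentence adds to the doubt, because its only mention of the visit sits inside the R-wave alternative. If the pacing threshold had no fixed visit, half of the composite would be open to choice after the data are seen.

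**Working it through.** This is mainly a comparison of texts. A short calculation then shows what does and does not depend on the wording.

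**1. Which texts set the time point**

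| Place | Time point | Role |
|---|---|---|
| Synopsis (2.0) | through 6 months | one-line summary |
| 6.2 | through 6 months | one-line summary |
| 6.2.1.2, lead sentence | 6-month visit, both measures | definition |
| 6.2.1.2, success sentence, threshold limb | none named | scoring rule |
| 6.2.1.2, success sentence, R-wave limb | 6-month visit, with the implant value as alternative comparator | scoring rule |
| 6.2.1.2, heading over the hypotheses | 6 months | test |
| 6.2.1.3 | 6 months | test |

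Every text that defines or tests the endpoint and names a time gives 6 months. The other wording occurs only in the two summary lines. Those lines do not require values to be in range at every visit, and they give no rule for classifying a subject.

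**2. What the summary wording most likely means**

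Section 6.2 describes the study objective with the same preposition, covering the period from implant to 6 months. It also words the supplementary effectiveness endpoint as running through 1 year, while sections 6.2.3 and 6.2.3.3 evaluate that endpoint at 12 months. The pattern is consistent: the summaries name the follow-up period and the detailed sections name the evaluation time. The visit-by-visit tabulation in 6.2.1.2 also means that values over the whole period are reported, outside the success rule.

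**3. The pacing threshold's visit**

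The success sentence alone does not give it. Three other visible places do: the lead sentence, which covers both measures; the heading over the hypotheses; and 6.2.1.3. The confidence interval in 6.2.1.2 is for conformance with the threshold and R-wave criteria together, so the two limbs are scored as one composite under that 6-month heading. An analyst would use the month-6 threshold.

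**4. What the test requires**

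Inputs from 6.2.1.2: n = 300, goal 85.0%, lower limit of an exact two-sided 95% interval. With x successes, the lower limit is the 0.025 quantile of Beta(x, 300 − x + 1).

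- x = 267: 0.8490, fails.
- x = 268: 0.8528, passes.

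The pass mark is 268/300 = 89.3%. The expected rate and power behind n = 300 are blacked out, so the sample size itself cannot be reproduced. The pass mark needs neither, and rewording the summaries does not move it.

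**5. What would be at stake if the every-visit reading were the rule**

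This is illustration only, because the documents give no rates. Assume a true month-6 rate of 92%, with 3% of subjects in range at month 6 but out of range earlier. The every-visit rate is then 92% − 3% = 89%.

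- P(X ≥ 268 | n = 300, p = 0.92) = 0.960
- P(X ≥ 268 | n = 300, p = 0.89) = 0.473

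At an assumed month-6 rate of 96% and the same 3% share, the two probabilities are 1.000 and 0.993. The readings can therefore differ materially when the true rate is near 92% and hardly at all when it is high. The difference belongs to a rule that no visible scoring text adopts.

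**The case for a change.** The best case for acting is that the words differ in both places where the plan summarises its primary endpoint, that the literal meanings are different estimands, and that aligning them would cost a few words and no power. All of that is accurate. The success sentence is also the line a programmer would code from, and it should ideally carry the visit for both limbs.

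What does not stand is the step from untidy wording to a defect in the analysis. An analyst choosing between the readings has a definition, a test heading and an analysis section on one side, and two summary lines without a rule on the other. Nor does the threshold's timing hang on a single sentence, as step 3 of the working shows. The blacked-out text after the success sentence may state the visit outright, so a firm claim that it is missing would go beyond what can be seen.

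The reporting harm is possible but speculative. Section 22.0 says only that "results will be posted on ClinicalTrials.gov as required"; it does not say in which words. Anyone reporting the result has the definition in 6.2.1.2 to report from.

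**Conclusion.** No change to the plan follows. The synopsis and section 6.2 describe the primary effectiveness endpoint loosely, and the success sentence places its visit phrase awkwardly. Both are clerical points that the operative text resolves: pacing threshold and R-wave amplitude are assessed together at 6 months, with the implant R-wave as the alternative comparator.

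On that reading the effect on the analysis is nil. The goal stays at 85.0%, the test stays exact binomial, n stays at 300 and the pass mark stays at 268. The probabilities in step 5 of the working rest on assumed rates and describe an every-visit rule that the visible plan does not use, so they are no measure of a fault.

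The conclusion rests on the visible text of 6.2.1.2 and 6.2.1.3 and on nothing in the blacked-out blocks contradicting it. It covers timing only, not how subjects with replaced devices or missing measurements are scored.

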6.2.3.2 Supplementary Effectiveness Endpoint Evaluation at 12 Months

$H_0: \text{Rate} \leq 85.0\%$ vs. $H_1: \text{Rate} > 85.0\%$

A sample size of 600 subjects [REDACTED] establishing a two-sided 95% confidence interval for successful sensing and pacing, with a lower bound exceeding 85.0%, based on an exact binomial distribution.

The inability to sense or pace within the programmable range available in the Nanostim device, resulting in device repositioning, replacement, or removal will also be captured in the associated safety endpoints.

Clinical Investigation Plan

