6.4.4 Nanostim™ LP Retrievals and Replacement

When considering Nanostim™ LP retrieval and replacement, investigators will refer to the respective IFUs.

Under normal operating conditions, the Nanostim™ LP battery is expected to last for approximately 8 years. In the event a Nanostim™ LP must be removed during the clinical study follow-up period, investigators may opt to replace LPs in the following ways:

- Retrieve the first Nanostim™ LP and implant a new Nanostim™ LP,
- Deactivate the first Nanostim™ LP and implant a second Nanostim™ LP in close proximity to the first one, or
- Deactivate the first Nanostim™ LP and implant a traditional pacemaker or ICD with a lead.

Complete and submit the following case report forms and device print outs to St. Jude Medical, Sylmar, CA using the EDC system.

- System Revision Form
- Healthcare Utilization Form
- Nanostim™ LP Assessment and Programming Form, if applicable
- Adverse Event Form, if applicable
- Deviation Form, if applicable
- Death Form, if applicable
- Study Withdrawal Form, if applicable
- Product out of Service Form, if applicable

If the subject has the Nanostim™ LP removed at any time during the study, and the subject will not receive a replacement Nanostim™ LP, follow the subject for 30 days, and withdraw the subject from the study. Complete and submit the following case report forms to St. Jude Medical, Sylmar, CA using the EDC system.

- Study Withdrawal Form
- Product Out of Service Form

Clinical Investigation Plan

- Nanostim™ LP Assessment and Programming Form, if applicable
- Adverse Event Form, if applicable
- Deviation Form, if applicable
- Death Form, if applicable

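### Do the 6-month and 12-month effectiveness sections score subjects whose device is revised for lost pacing or sensing in conflicting ways?

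*Combined protocol and SAP*

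**What the plan says.** **The operative rule.** Section 6.2.1.2 ties the endpoint to one visit: "The composite primary effectiveness endpoint will be used to evaluate pacing thresholds and R-wave amplitudes at the 6-month visit". A subject succeeds if the pacing threshold and the R-wave amplitude meet stated limits; the R-wave limb can also be met by comparison with the value at implant. The same section adds a descriptive display: "Pacing thresholds and R-wave amplitudes will be collected, tabulated for each visit, and also displayed as frequency plots". The test is an exact binomial test of 300 subjects against 85.0%, with 600 subjects against 85.0% at 12 months (6.2.3.2).

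**Device revision.** Section 6.2.1.2 says that inability to sense or pace "resulting in device repositioning, replacement, or removal will be captured in the associated safety endpoints". Section 6.2.3.2 has "resulting in device repositioning, replacement, or removal will also be captured in the associated safety endpoints".

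**Summary lines.** Section 6.2, like the synopsis at 6 months, describes the endpoints in one sentence each: "The primary effectiveness endpoint evaluates pacing thresholds and R-wave amplitudes within the therapeutic range through 6 months post-implant" and "The supplementary effectiveness endpoint evaluates pacing thresholds and R-wave amplitudes within the therapeutic range through 1 year post-implant".

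**What can happen to the subject.** Section 6.4.4 allows the investigator to "Retrieve the first Nanostim™ LP and implant a new Nanostim™ LP", or to deactivate the first device and implant a second one or a conventional system. If the device is removed and no new one is given, the site is to "follow the subject for 30 days, and withdraw the subject from the study".

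**What cannot be read.** Two redacted blocks lie between the success criteria and the sentence on revision in 6.2.1.2. The definitions of the ITT and PP populations in 6.2.1.3 are redacted, as are three blocks at the end of that section.

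**The concern.** A subject whose device loses pacing or sensing and has to be replaced at month 2 is as plain an effectiveness failure as this trial can produce. Three features of the visible text suggest that such a subject might escape the effectiveness count:

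- The 12-month sentence has *also*, which presupposes that the event counts in effectiveness too. The 6-month sentence lacks the word, so it could be read as safety instead of effectiveness.
- The summary lines speak of performance *through* 6 months, under which the subject fails. The operative rule looks only at the 6-month reading, which may come from a second device and be in range. There are then two candidate implant values for the R-wave comparison.
- A subject withdrawn 30 days after an early removal has no 6-month reading and could drop out of the denominator.

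If that happened, the test against 85% would describe only devices that survived to the visit. The safety endpoint would be a weak substitute, because its goal tolerates many complications.

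**Working it through.** **1. The sentences side by side.** Section 6.2.1.2: the event is captured in safety. Section 6.2.3.2: the event is also captured in safety. Both are satisfied by a rule under which the event counts in safety and the subject is scored in effectiveness by whatever rule applies there. A contradiction needs an *only* or an *instead* in 6.2.1.2, and there is none.

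**2. Through versus at.** Section 6.2.1.2 supplies limits, a time point and a success definition; the lines in 6.2 and the synopsis supply none of these. The detailed section governs, and an analyst would program from it. The word *through* does not itself say that every earlier revision is a failure.

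**3. Device removed, no reading.** The success criterion is conditional on values in range at the visit. A subject without a reading does not satisfy it, and ITT is one of the two populations in which the endpoint is evaluated. The visible text therefore leans towards not met, with exclusion as the departure.

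**4. Does safety catch the event?** In 6.2.5 a complication is a device- or procedure-related serious adverse event, and the serious definition includes events that need an invasive strategy to remedy. Catheter retrieval or a new implant fits that description.

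**5. How much could the score matter?** Inputs: n = 300 and goal 85.0% (6.2.1.2); n = 600 and goal 85.0% (6.2.3.2); two-sided 95% exact interval. The redacted assumptions mean that the planned 300 cannot be reproduced, but the pass mark can. The lower bound for x successes in n is the 0.025 quantile of Beta(x, n − x + 1).

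- 268/300 gives 0.8528 (pass); 267/300 gives 0.8490 (fail).
- At n = 600 the pass mark is 528 (lower bound 0.8513).

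Assumed share f of subjects with such an event: 1%, 2%, 4%. The documents give no rate; section 13.5 cites about 96% event-free at 6 months for conventional pacemakers, so 4% corresponds to any event there, a wider class than this one. Let the true success rate, with these subjects as failures, be exactly 0.85.

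- Counted as failures: P(Bin(300, 0.85) ≥ 268) = 0.0183.
- Left out: P(Bin(300(1 − f), 0.85/(1 − f)) ≥ pass mark).
- Replaced and scored as success: P(Bin(300, 0.85 + f) ≥ 268).

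| f | Pass mark if left out | Counted | Left out | Replaced, success |
|---|---|---|---|---|
| 1% | 265/297 | 1.8% | 5.3% | 5.3% |
| 2% | 263/294 | 1.8% | 9.6% | 13.1% |
| 4% | 257/288 | 1.8% | 39.9% | 47.3% |

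At n = 600 the same steps give 2.0% counted; 6.8%, 21.6%, 68.1% left out; and 8.6%, 25.5%, 80.3% replaced.

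**6. Cost of a strict failure rule.** With 92% in range among measured subjects, power at n = 300 if the events are left out is P(Bin(300(1 − f), 0.92) ≥ pass mark) = 96.5%, 95.2%, 96.2%. If they count as failures it is P(Bin(300, 0.92(1 − f)) ≥ 268) = 87.6%, 72.4%, 33.1%. With 95% in range, the strict rule keeps 99.9%, 99.4%, 89.1%.

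**7. Safety as a backstop.** 270/300 free of complications gives a lower bound of 0.8603 (pass); 269/300 gives 0.8565 (fail). So 300 − 270 = 30 complications still meet the 86% goal.

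**The case for a change.** The strongest case for a change is that the scoring of these subjects should not have to be inferred. A replaced device can be in range at 6 months, so a subject can pass under the visit rule and fail under a literal reading of *through*. No visible text says which implant value applies after a replacement. Safety does not compensate, since 30 complications among 300 are tolerated. Stating a rule would take two sentences and no new data, because revisions and withdrawals are already recorded.

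Part of this stands. The wording is uneven, no score for replaced devices is visible, and the arithmetic shows that the score can affect the outcome if such events are not rare.

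It does not carry the conclusion, for three reasons. First, the redactions fall where the rule would be: directly after the success criteria, in the population definitions and at the end of 6.2.1.3. The missing-data section may be shortened as well, since 6.2.1.7 and 6.2.1.8 survive only as headings and 6.2.1.5 appears only in the contents. Silence in this copy is not evidence of silence in the plan. Second, for replaced devices, scoring the subject's pacing at the visit and counting the revision in safety is a defensible estimand; failing the subject outright is another. Preferring the second is a judgement, and it costs power. Third, the striking percentages come from the 4% case with a true rate of exactly 85%; at 1% and 300 subjects the figure is 5.3%.

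**Conclusion.** The passages do not conflict. The 6-month and 12-month sentences differ by one word, both send the event to safety and neither scores effectiveness; the *through* lines are short summaries of a visit-based rule. That is a drafting slip with no effect on the analysis as specified. For a removed device without a reading, the visible criterion together with the ITT analysis already points to not met. For a replaced device, the score is an estimand choice that may be settled in the redacted text.

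The possible size is real but conditional. At 300 subjects and a true rate of 85%, leaving these subjects out would raise the chance of passing from 1.8% to between 5.3% and 39.9%, for assumed event shares of 1% to 4%. Against that, a strict failure rule would lower power from 96.2% to 33.1% in the 4% case with 92% in range. Both ranges rest on event rates that the documents do not give. No change to the plan follows.
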